7.8.3 Vital signs

The analyses of vital signs (blood pressure, pulse rate, body temperature) will be descriptive in nature. Descriptive statistics of vital signs over time and for the difference from baseline (see Section 6.7) will be provided.

Body weight will only be listed.

Clinically relevant findings in vital signs data will be reported as baseline conditions (at screening) or as AEs (during the trial) if judged clinically relevant by the investigator, and will be analysed as such.

7.8.4 ECG

12-lead ECG

Abnormal findings will be reported as baseline conditions (at screening) or as AEs (during the trial) if judged clinically relevant by the investigator.

All evaluation of ECG data except of exposure response analysis will be based on the TS. The exposure-response analysis will then be done on the ECGPCS.

Listing of individual data

For all quantitative endpoints, listings of individual data will be shown in Appendix 16.2. Occurrences of notable findings (as defined in [Section 5.3.2](#)) will be flagged.

For all subjects with any notable finding in quantitative ECG recordings, a separate listing will be created as end-of-text display (based on the same display template as in Appendix 16.2), and the corresponding time profiles will be shown.

Comments regarding the ECGs will be listed.

Descriptive analysis

Descriptive statistics (N, mean, SD, min, median, max) will be provided for the changes from baseline over time in all quantitative ECG variables, and time profiles of mean and SD for the changes from baseline on treatment will be displayed graphically by treatment.

Plasma concentrations and relationship to QTcN, QTcF, QT interval and HR change from baseline

For the following analyses, all time points with ECG recordings with centralised evaluation and corresponding plasma concentrations will be included.

The changes from baseline in QTcN (Δ QTcN) will be investigated as response variable. The placebo subjects will be included in the analysis, with zero plasma concentrations. Time points with plasma concentrations "BLQ" in subjects in active dose groups will be ignored in this analysis.

As a first step, it will be investigated if there is a potential delayed or accelerated (e.g. metabolites) effects of the drug on QTcN. A general visual impression of the PK-QT relationship is provided by overlaying time profiles of plasma concentrations and QTcN changes from baseline (Δ QTcN). All figures will be generated for each subject (presented in Appendix 16.1.9.2 of the CTR), as well as for means per active treatment (presented in Section 15.3 of the CTR).

In case of non-linearity or if there is evidence for a delayed effect, further models will be explored that better characterise the PK/ECG relationship (effect compartment, non-linear model etc.).

If there is no non-linearity or delayed effect seen, the relationship between BI 655130 plasma concentrations and QTcN changes from baseline will be investigated in an exploratory manner using a random coefficient model approach to estimate the QTcN change from baseline and its 90% confidence interval at the geometric mean of the C_{max} for each dose (multiple dose groups as well as single dose group). Additionally, the estimated slope with its 90% confidence interval will be provided. The used random coefficient model is based on Garnett et al. 2016 [R17-0553] ([10](#)):

```
PROC MIXED DATA=myDATA METHOD=REML;
CLASS subject active(ref=FIRST) time;
MODEL ECGep = conc active time / NOINT CL ALPHA=0.1 ALPHAP=0.1 DDFM=KR
    OUTPREDM=pred;
RANDOM INT conc / TYPE=UN SUBJECT=subject;
ESTIMATE 'Pred. value at conc. xx.xx' conc xx.xx active 1 -1 / CL
    ALPHA=0.1;
ESTIMATE 'Slope estimate' conc 1 / CL ALPHA=0.1;
RUN;
```

Here "ECGep" is the QTcN change from baseline, "active" is a dummy 0/1 variable indicating the active treatment (1=active, 0=placebo), "conc" is the corresponding plasma concentration value of the drug, and "xx.xx" is the given concentration value (i.e. the value of the geometric mean C_{max} of a given dose group). The class variable "time" is the time relative to the most recent infusion; here, measurements at time points at the end of infusion will not enter the model with the planned time, but only by means of the time points defined in [Table 6.7: 3](#). The "TYPE=UN" option causes the two specified random coefficients to have a bivariate normal distribution. In case of convergence problems see [Section 9.2](#) for possible improvements (option "TYPE=FA0(2)" may also be used as a potential solution, it requests a G matrix estimate that is constrained to be nonnegative definite). If the note "estimated G matrix is not positive definite" occurs in the SAS log file, the random slope "conc" might be removed from the "RANDOM" statement. When the plasma concentrations are not normally distributed, the exposure-response model can be applied to $\log(\text{conc})$ instead of the raw concentration.

For visualization, the BI 655130 plasma concentration against the response will be plotted as well as the (fixed effect) regression line, its 90% confidence interval and the geometric mean of C_{max} for each dose. For each subject and each time point, subtract the mean value of all individual observed ΔQTc values from the placebo group for this time point from the individual observed ΔQTc value for this subject and time point. This results in estimates for "individual $\Delta\Delta QTc$ " values. These estimates should only be used for plotting purposes.

All of the above described graphical and statistical analyses will be also performed for QTcF, HR and QT in place of QTcN.

Categorical Endpoints

For the categorical endpoints, frequency tables will be provided.

For subjects with notable findings, the individual time courses of QTcN, QTcF, QT, HR, PR, and QRS of these subjects will be presented in figures.

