##### Multiple dose part (3 mg/kg, 6 mg/kg, 10 mg/kg, 20 mg/kg b.w.):

[figure not shown]
After the first dose:

- $AUC_{\tau,1}$  (area under the concentration-time curve of the analyte in plasma over a uniform dosing interval  $\tau$  after administration of the first dose)
- $C_{max}$  (maximum measured concentration of the analyte in plasma)

After the last dose:

- $AUC_{\tau,ss}$  (area under the concentration-time curve of the analyte in plasma at steady state over a uniform dosing interval  $\tau$ )
- $C_{max,ss}$  (maximum measured concentration of the analyte in plasma at steady state over a uniform dosing interval  $\tau$ )

Proprietary confidential information © 2017 Boehringer Ingelheim International GmbH or one or more of its affiliated companies

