2. LIST OF ABBREVIATIONS

Term	Definition / description
ADPC	Proper name of the analysis dataset containing PK concentrations per time-point or per time-interval
ADPP	Proper name of the analysis dataset containing calculated PK parameters
ADS	Analysis dataset
AE	Adverse event
AESI	Adverse event of special interest
AIC	Akaike's information criterion
ALT	Alanine aminotransferase
AST	Aspartate aminotransferase
AUC _{0-∞}	Area under the concentration-time curve of the analyte in plasma over the time interval from 0 extrapolated to infinity
AUC _{τ,ss}	Area under the concentration-time curve of the analyte in plasma at steady state over a uniform dosing interval τ
AUC _{τ,1}	Area under the concentration-time curve of the analyte in plasma over a uniform dosing interval τ after administration of the first dose
AUEC _{above}	Area above the biomarker effect vs. time curve above the baseline during the treatment interval
AUEC _{below}	Area under the biomarker effect vs. time curve below the baseline during the treatment interval
AUEC _{diff}	Difference between AUEC _{below} and AUEC _{above}
BI	Boehringer Ingelheim
BLQ	Below the lower limit of quantification
BMI	Body mass index
BMS	Biomarker set
CARE	Clinical data analysis and reporting environment
CI	Confidence interval
C _{max}	Maximum measured concentration of the analyte in plasma after administration of the first dose
C _{max,ss}	Maximum measured concentration of the analyte in plasma at steady state
CRF	Case report form

Term	Definition / description
CTP	Clinical trial protocol
CTR	Clinical trial report
CV	Arithmetic coefficient of variation
DBLM	Database lock meeting
E_{base}	Baseline effect of biomarker
ECG	Electrocardiogram
ECGPCS	Electrocardiogram plasma concentration set
eCRF	Electronic case report form
EMA	European Medicines Agency
E_{max}	Maximum effect of biomarker
EudraCT	European union drug regulating authorities clinical trials
gCV	Geometric coefficient of variation
gMean	Geometric mean
HR	Heart rate
ICH	International Council for Harmonisation of Technical Requirements for Pharmaceuticals for Human Use
IPV	Important protocol violation
MD	Multiple dose
MedDRA	Medical Dictionary for Regulatory Activities
NOA	Not analysed
NOP	No peak detectable
NOR	No valid result
NOS	No sample available
on-trt	on-treatment
PD	Pharmacodynamic(s)
PK	Pharmacokinetic(s)
PKS	Pharmacokinetic parameter analysis set
PR interval	ECG interval from the onset of P wave to the beginning of the QRS
PV	Protocol violation

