5.2.2 Secondary endpoint

Secondary endpoints in the single dose part of this trial are $AUC_{0-\infty}$ and C_{max} of BI 655130 in plasma.

Secondary endpoints in the multiple dose part of this trial are $AUC_{\tau,1}$, C_{max} , $AUC_{\tau,ss}$ and $C_{max,ss}$ of BI 655130 in plasma, as defined in Section 5.5.1.1 of the CTP.

[REDACTED]

[REDACTED]

[REDACTED]

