6.7 BASELINE, TIME WINDOWS AND CALCULATED VISITS

6.7.1 Time points and baseline for analysis of 12-lead ECG

There will be a centralised evaluation of all 12-lead ECG recordings at the time points specified in Table 6.7: 1 below:

Table 6.7.1: 1 Time schedule of 12-lead ECG recordings with centralised evaluation

Visit	Day	Planned time [hh:mm] (relative to respective drug administration)	Comment ²	Study phase
2	1, 8 ¹ , 15 ¹ and 22 ¹	-02:00		Baseline/on-trt ³
		00:30	only for BI 3 mg/kg MD, 6 mg/kg MD and BI 20 mg/kg SD	On-treatment
		01:00	only for BI 10 mg/kg MD and BI 20 mg/kg SD	
		01:30	only for BI 20 mg/kg MD and BI 20 mg/kg SD	
		02:00		
		03:00	only for BI 20 mg/kg SD	
		04:00	only for BI 20 mg/kg SD	
		06:00		
		08:00	only for BI 20 mg/kg SD	
		12:00		
2, 9 ¹ , 16 ¹ and 23 ¹		24:00		
		32:00	only for BI 20 mg/kg SD	
3, 10 ¹ , 17 ¹ and 24 ¹		48:00		

¹ These days are only applicable to dose groups with multiple dosing

² If no comment is given, time point is applicable to all dose groups in this trial

³ ECG recording at relative time -2:00 h prior to next dosing is considered to be baseline on Day 1 and to be on-treatment on other days

Triple ECGs (3 single ECGs recorded within 180 sec) will be recorded on all time points with centralised ECG evaluation (as listed in the table above). On all other time points, single ECGs will be recorded.

The value of an ECG variable at each of the time points with triple ECG is defined as the arithmetic mean of the 3 single ECG measurements. In particular, the baseline value of an ECG variable is defined as the mean of the triple ECG measurements prior to first drug administration.

For the exposure-response analysis, ECG measurements and corresponding plasma concentrations building pairs using the same planned time points will be used (e.g., QTcN change from baseline and plasma concentration for planned time 0:30 will build one pair.) Whether a time deviation between a PK sample and the corresponding ECG recording is too big and the respective pair has to be excluded, or whether a value has to be matched to another time point, will be decided no later than at the RPM/DBLM.

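### For the multiple-dose groups, the concentration-QTc predictions and plot markers are set at first-dose Cmax, so none describes the highest exposure in the trial

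*SAP*

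**What the plan says.** SAP 7.8.4 (ECG) fits a random coefficient model of the QTcN change from baseline on plasma concentration. It then reports the predicted change and its 90% "confidence interval at the geometric mean of the C_{max} for each dose (multiple dose groups as well as single dose group"). The prediction comes from the statement "ESTIMATE 'Pred. value at conc. xx.xx' conc xx.xx active 1 -1 / CL", where the inserted concentration is the geometric mean Cmax of the dose group. The regression plot shows the fitted line, "its 90% confidence interval and the geometric mean of C_{max} for each dose". The same analyses are repeated for QTcF, HR and QT.

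The SAP's list of abbreviations (Section 2) defines Cmax as "Maximum measured concentration of the analyte in plasma after administration of the first dose". It defines Cmax,ss separately as "Maximum measured concentration of the analyte in plasma at steady state". The endpoint sections make the same split for the multiple-dose part. Protocol 5.5.1.1 lists Cmax after the first dose and, after the last dose, Cmax,ss as the "maximum measured concentration of the analyte in plasma at steady state over a uniform dosing interval". SAP 5.2.2 names Cmax and then, as a separate item, AUC at steady state "and $C_{max,ss}$ of BI 655130 in plasma, as defined in Section 5.5.1.1 of the CTP". Cmax,ss does not appear in SAP 7.8.4.

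**The concern.** The predicted rows are the summary a reader will use to judge the QTc effect at each dose. Read with the SAP's own definition, a programmer would insert first-dose values for the multiple-dose groups. Those groups accumulate drug over four weekly infusions, so their highest concentrations follow the Day 22 infusion.

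The 20 mg/kg multiple-dose group is the only one that reaches the top exposure, and Protocol 2.2 gives a wider safety window as the reason for studying it. Its row would nearly repeat the 20 mg/kg single-dose row. The table would have no estimate with a confidence interval at the exposure that distinguishes the group.

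**Working it through.** The plan gives no figure for this point, so there is none to reproduce. The check is one of definitions, followed by the likely size of the gap.

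**Inputs from the documents.** Infusions on Days 1, 8, 15 and 22, so the interval is 7 days (Protocol 3.1). Half-life about 4 weeks, preliminary and from the earlier single-dose trial (Protocol 11, rationale for amendment 1). Top dose 20 mg/kg in both parts (Protocol 3.1). Any distribution phase is assumed, because the documents give none.

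**Accumulation.** R4 is the fourth-dose peak divided by the first-dose peak, by superposition.

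- One compartment, half-life t days: R4 = sum over k = 0 to 3 of 2^(-7k/t). At 28 days this is 1 + 0.841 + 0.707 + 0.595 = 3.14.
- Fraction f of the peak lost with an assumed 2-day half-life, the rest with 28 days: R4 = sum over k = 0 to 3 of [f x 2^(-7k/2) + (1-f) x 2^(-7k/28)].
- 60% gone by Day 7, then 28-day decay: R4 = 1 + 0.4 x (1 + 0.841 + 0.707) = 2.02.
- Only a share B of the peak persists to the next dose: R4 = 1 + B x sum over i = 1 to 3 of 2^(-7i/t).

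| Assumption | R4 | 1/R4 |
|---|---|---|
| One compartment, 35 d | 3.29 | 0.30 |
| One compartment, 28 d | 3.14 | 0.32 |
| One compartment, 21 d | 2.92 | 0.34 |
| f = 0.25 | 2.63 | 0.38 |
| f = 0.45 | 2.22 | 0.45 |
| 60% gone by Day 7 | 2.02 | 0.50 |
| f = 0.70 | 1.71 | 0.58 |
| B = 0.2, 28 d | 1.43 | 0.70 |
| B = 0.2, 14 d | 1.31 | 0.76 |

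R4 exceeds 1 in every case.

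**Where the rows fall.** Scale the 20 mg/kg first-dose peak to 1 and assume dose-proportional peaks. The planned rows are then at 0.15, 0.30, 0.50 and 1.00 for 3, 6, 10 and 20 mg/kg multiple dose, and at about 1.00 for 20 mg/kg single dose. The 90-minute and 60-minute infusions change the end-of-infusion peak by at most 0.3% in the infusion cases run. Fourth-dose peaks are d x R4/20:

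- R4 = 3.14: 0.47, 0.94, 1.57, 3.14
- R4 from 1.31 to 3.29: 0.20-0.49, 0.39-0.99, 0.66-1.64, 1.31-3.29

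The 20 mg/kg fourth-dose peak is above every planned row throughout. The 10 mg/kg peak is also above them once R4 exceeds 2.

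**Effect on a predicted row.** Under the linear model a row is slope x concentration + (active minus placebo). Only the first part scales.

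- As written, the 20 mg/kg multiple-dose row shows 1/R4 of the fourth-dose slope part: 30% to 58% for R4 from 3.29 to 1.71, and 76% at 1.31.
- The amount missing is slope x (R4 - 1) x first-dose Cmax. The active term cancels.
- Illustration only: if the slope part were 10 ms at the fourth-dose peak, the row would fall short by 10 x (1 - 1/R4), which is 6.8 ms at 3.14, 4.15 ms at 1.71 and 2.4 ms at 1.31.

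This scaling does not carry over to the log-concentration or non-linear options that 7.8.4 allows.

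**Share of steady state after four doses** (one compartment): 1 - 2^(-28/t) = 60%, 50% and 43% at 21, 28 and 35 days. This bears on the fix.

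**The case against.** **The authors may have meant the overall maximum.** Section 7.8.4 does not itself say first dose, and the protocol's abbreviation list defines Cmax with no dose qualifier. That is possible. But the SAP's own definition says first dose, both endpoint sections keep the two parameters apart, and nothing in 7.8.4 overrides this. If the overall maximum was meant, the text still has to say so.

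**Little information is lost.** This largely stands. The ECG schedule in SAP 6.7.1 includes Days 8, 15 and 22 ("These days are only applicable to dose groups with multiple dosing"), and all matched pairs enter the model. The slope with its interval, the regression line and band, the summaries by time and the categorical tables are unaffected. The code also saves fitted means with 90% limits for every record. Those saved values are not placebo-corrected, however, and the SAP does not say that they will be tabulated. The interval for a row cannot be rebuilt from the slope interval alone, because the ESTIMATE statement also contains the active-minus-placebo term.

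**The analysis is exploratory, and the rows arise only if no non-linearity or delay is seen.** Both are true, and they limit the weight of the point.

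**The size rests on assumptions.** This stands. The half-life is preliminary, and Protocol 3.2 notes that the earlier trial did not test a 20 mg/kg infusion. The distribution-phase figures have no source in the documents. Only the direction should be relied on.

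**Conclusion.** The concern holds. On the SAP's own definition, the tabulated predictions and plot markers for the multiple-dose groups sit at first-dose Cmax, and none lies at the highest exposure reached. The direction follows from weekly dosing with a half-life of about 4 weeks. The size depends on kinetics the documents do not give: the fourth-dose peak is 1.31 to 3.29 times the first over the assumptions examined, and 3.14 times for one compartment at 28 days.

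The damage is confined to how the predicted rows and markers for QTcN, QTcF, QT and HR are read. The fit, the slope and the primary endpoint are unaffected, and no stopping rule uses these rows. It should be corrected because the affected rows are a stated output of the analysis and the correction is small.

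**What to change.** In SAP 7.8.4, state that for each multiple-dose group the predictions and plot markers are placed at the geometric mean of the maximum concentration measured after the fourth infusion (Day 22). Use Cmax,ss where that parameter is reported, and otherwise the measured Day 22 maximum. The second branch is needed because Protocol 7.1.1 makes attainment of steady state a precondition for steady-state parameters, and four weekly doses may reach only about half of steady state. Keep Cmax for the single-dose group. First-dose Cmax can stay as an optional extra row for the multiple-dose groups.

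The cost is one SAP sentence, one further ESTIMATE value per multiple-dose group for each of four ECG variables (4 x 4 = 16), and the plot markers. No new data and no refit are needed.

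### The exploratory concentration-QTc model has no baseline covariate, which costs some precision and leaves part of any chance baseline difference in the predictions at Cmax

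*SAP*

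**What the plan says.** SAP 7.8.4 gives the SAS code for the exposure-response analysis. The response "is the QTcN change from baseline". The fixed part is "MODEL ECGep = conc active time / NOINT CL ALPHA=0.1 ALPHAP=0.1 DDFM=KR", and the random part is "RANDOM INT conc / TYPE=UN SUBJECT=subject". Placebo subjects enter the same fit: "The placebo subjects will be included in the analysis, with zero plasma concentrations".

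Predictions at the geometric mean Cmax of each dose group come from "ESTIMATE 'Pred. value at conc. xx.xx' conc xx.xx active 1 -1 / CL". Each is therefore the slope times concentration plus the active-minus-placebo difference. They are reported with 90% confidence intervals, and the slope is reported as well. The SAP says the relationship "will be investigated in an exploratory manner using a random coefficient model approach". The same analysis is repeated for QTcF, HR and QT.

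On baseline, SAP 6.7.1 says that "the baseline value of an ECG variable is defined as the mean of the triple ECG measurements prior to first drug administration". The table in that section counts the pre-dose ECGs on Days 8, 15 and 22 as on-treatment. Baseline is not a covariate in the MODEL statement, in the explanation of its terms, in the convergence steps of SAP 9.2, or anywhere else in the SAP or protocol.

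**The concern.** A subject whose baseline is high by chance tends to show a smaller change afterwards, so change scores are negatively related to baseline. If the active group happens to start higher than placebo, its mean change is pulled down relative to placebo, and the reverse holds if it starts lower. A model without baseline attributes that pull to the `active` term, which is part of every prediction at Cmax.

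Two features of this trial make the point worth a line of code. The contrast rests on only 10 placebo subjects, so chance differences in mean baseline can be sizeable. And one triplicate serves as baseline for the whole trial, so its error enters every change score of that subject and further on-treatment ECGs cannot average it out. The random subject intercept represents the resulting within-subject correlation, but it does not adjust the contrast for a baseline difference.

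At stake are the precision of the model-based QT estimate and its position in a trial where an imbalance occurs. If active subjects start higher, the shift is towards understating a QT effect.

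**Working it through.** **Inputs from the documents.** Five dose groups of 6 active and 2 placebo (protocol 3.1) give 30 active and 10 placebo, 40 in total. The model has one 0/1 `active` indicator, and its subject set is drawn from all treated subjects (SAP 6.3), so the contrast is 30 against 10. The plan states no precision or power figure for this analysis, and protocol 7.6 says the sample size is not power-based, so there is no stated figure to reproduce.

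**Assumed inputs.** The documents give no QTc SDs. I take a between-subject SD (sb) of 10-20 ms and a within-subject SD of the triplicate mean (sw) of 5-10 ms.

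**Step 1: how much of an imbalance stays.** Let rho = sb²/(sb² + sw²) be the correlation between baseline and an on-treatment value. With no drug effect, change regresses on baseline with slope -(1 - rho), where 1 - rho = sw²/(sb² + sw²). A baseline difference D therefore leaves -(1 - rho) × D in the unadjusted contrast.

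**Step 2: how large a chance imbalance is.** SE(D) = sqrt(sb² + sw²) × sqrt(1/30 + 1/10) = 0.365 × sqrt(sb² + sw²).

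**Step 3: shift for a one-SE imbalance**, (1 - rho) × SE(D):

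| sb, sw (ms) | Total SD | 1 - rho | SE(D) | Shift (absolute) |
|---|---|---|---|---|
| 20, 5 | 20.6 | 0.059 | 7.53 | 0.44 |
| 15, 5 | 15.8 | 0.100 | 5.77 | 0.58 |
| 15, 8 | 17.0 | 0.221 | 6.21 | 1.37 |
| 20, 10 | 22.4 | 0.200 | 8.16 | 1.63 |
| 10, 8 | 12.8 | 0.390 | 4.68 | 1.82 |
| 10, 10 | 14.1 | 0.500 | 5.16 | 2.58 |

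The range is about 0.4-2.6 ms. It is widest where the baseline is least reliable.

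**Step 4: effect on precision.** The textbook variance ratio (1 + rho)/2 assumes one post-baseline value per subject, so it does not describe this repeated-measures model. Precision was simulated instead: 1,500 trials per setting, no true drug effect, 30 active and 10 placebo, a simplified ECG-PK schedule, a random subject intercept, known variances, and no random slope. The quantity below is the prediction at the Cmax of the 20 mg/kg multiple-dose group.

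| sb, sw | SD without baseline | SD with centred baseline | Reduction | ms per ms of imbalance, without → with |
|---|---|---|---|---|
| 20, 6 | 2.73 | 2.67 | 2% | -0.09 → 0.00 |
| 15, 5 | 2.19 | 2.10 | 4% | -0.11 → -0.01 |
| 15, 8 | 3.57 | 3.34 | 6% | -0.21 → 0.01 |
| 10, 8 | 3.59 | 3.08 | 14% | -0.39 → 0.00 |
| 10, 10 | 4.67 | 3.81 | 18% | -0.51 → -0.02 |

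**Step 5: conditional and average behaviour.** I looked at the fifth of simulated trials with the highest active-minus-placebo baseline. At sb 15, sw 8 (mean imbalance 8.7 ms) the mean estimate was -1.6 ms without baseline and +0.2 ms with it. At sb 10, sw 10 (mean imbalance 7.2 ms) it was -3.8 and -0.2 ms. The true value is 0 in both. Over all trials, both models averaged within about 0.2 ms of 0. The slope-times-Cmax part depended on imbalance by about 0.03 ms per ms or less, so the shift sits in the `active` contrast.

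**The case against.** The strongest reply is that the planned model is valid as it stands. Active and placebo are randomised within dose groups (protocol 7.5), so regression to the mean cancels in expectation in the placebo contrast. Chance variation in change between subjects is carried by the random intercept and already contributes to the width of the 90% interval. The change score removes most or at least half of any imbalance under the assumed SDs. Averaging three ECGs of four cardiac cycles each (SAP 6.7.1 and 9.1) reduces baseline noise further. At the low end of the range, 0.4 ms is negligible beside an estimate whose SD is 2 to 5 ms. All of this stands. It bounds the size of the point, but it does not remove the gain or name a cost of adjusting.

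The SAP also says its model is based on a published paper. That paper is not available here, so it counts for neither side.

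A reader might infer three stronger things:

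- **That the estimate is biased or its interval invalid.** The simulations show no average bias under randomised allocation. The single-dose part is only partially randomised (protocol 3.1), but nothing in the documents suggests that baseline QTc differs between its cohorts.
- **That the trial's QT conclusion is at risk.** SAP 7.8.4 calls the analysis exploratory and sets no decision threshold. QT is also assessed by categorical endpoints, notable findings and descriptive changes. The dose-escalation rule in protocol 3.3.4.2 uses individual QT and QTc values.
- **That the exposure-response slope is distorted.** It is almost untouched.

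**Conclusion.** The point holds as a modest improvement to an exploratory estimate. Leaving baseline out of the model costs some precision and makes the placebo-corrected prediction at Cmax depend on whatever baseline imbalance occurs between 30 active and 10 placebo subjects.

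Under assumed SDs of 10-20 ms between and 5-10 ms within subjects, a one-SE imbalance shifts the prediction by about 0.4-2.6 ms. Over similar values, adjustment lowers the SD of the estimate by about 2-18%. The millisecond figures rest wholly on those assumptions. The precision figures also rest on a simplified simulation with known variances and independent errors between time points. If baseline QTc proves very reliable, the gain will be close to nil. Severity is low.

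**What to change.** In SAP 7.8.4, add one fixed covariate to the PROC MIXED model: the subject's triplicate baseline of the variable being modelled, minus the overall mean baseline of that variable. Use baseline QTcN in the QTcN model, and likewise for QTcF, QT and HR. The ESTIMATE statements need no change, because baseline is held equal in an active-minus-placebo contrast and does not enter the slope.

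The cost is one model term and one parameter. No new data are needed, and no subject is lost, since a subject without a baseline has no change score either. If the team prefers to keep the present model as the main one, the adjusted fit can be pre-specified as a sensitivity analysis. Either way it should be settled before the ECG results are examined by treatment, so that the choice between the two fits does not follow an observed imbalance.
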